1.2 Secondary Objectives

Utilization (emergency room visits and hospitalizations) for patients in both arms will be tracked and reviewed at regular intervals throughout the study period. Utilization is defined in terms of specialty visits, emergency room visits, and hospitalizations up to 12 months following the screening visit. This will be tracked via the EMR in both groups.

2 **BACKGROUND AND RATIONALE**

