2. Tests ordered for reversible causes of cognitive impairment as recommended by the published guidelines of professional societies (e.g. thyroid function tests, B-12 level, CT or MRI scans).^{15, 38-41}
3. New prescriptions for dementia medications in EMR.
4. Referral for cognitive/dementia evaluation by specialists (Neurology, Geriatrics or Psychiatry) in EMR.

Secondary/exploratory outcomes: Health care utilization data (*secondary outcome*) is abstracted from EMR. Additional tests (described below) take approximately 60 minutes of participants’ time. To avoid interrupting clinic flow, these tests will be done at the same visit as the enrollment, but after the patient sees their clinician. These tests are *exploratory outcomes* used to generate new hypotheses or provide insights into 5-Cog efficacy.

- a) **Health care utilization (secondary outcome):** Utilization (emergency room visits and hospitalizations) for patients in both arms will be tracked up to 12 months from the clinic visit at which the patient was randomized and reviewed at regular intervals by data analysts throughout the study period. The data analysts will have no participant contact and be blinded to study assignment. The EMR system is in place in our institution. All visit notes and diagnoses are to be entered within 48 hours of the encounter. A series of electronic reminders is sent to clinicians to complete delinquent entries. Patients in both arms will be covered by risk or shared savings reimbursement arrangements Montefiore has with private health insurance companies or will be fee-for-service Medicare beneficiaries attributed to the Montefiore Next Generation Accountable Care Organization.⁴²⁻⁴⁴ Montefiore either processes or has access to claims data for these patients, enabling analysis of encounters and costs through the Montefiore EMR and reports received monthly from CMS. The detailed claims-level data will allow for tracking and analysis of the utilization of numerous healthcare services. A significant amount of data on care and services that patients receive from providers outside of Montefiore will also be available for inclusion in our analyses.

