- *Over- or under-detecting cognitive impairment:* Given the high sensitivity and validity of 5-Cog procedures for dementia detection, we do not expect under-detection to be a major issue. We will set PMIS cutscores to maximize sensitivity and will improve cognitive concern ascertainment. A major consequence of over-detection is the strain on limited primary care resources resulting from more dementia assessments. Our decision tree provides guidance to primary care physicians regarding next steps in cognitively impaired patients. Red flags are built within our decision tree to channel patients for specialist evaluations. These steps were developed in consultation with our primary care partners. We will carefully monitor clinical, logistical and economic impact of introducing 5-Cog in our primary care sites, and make any necessary system changes to optimize clinical encounters. It is encouraging that introducing PMIS into our local EMR has not resulted in significant bottlenecks or overburdening specialists. We have also not observed any significant bottlenecks or negative feedback from primary care staff regarding implementing the first phase of the 5-Cog battery at our site.

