9.4.2 Secondary outcomes

Health care utilization (emergency room visits and hospitalizations) for patients in both arms will be tracked up to 12 months from the clinic visit at which the patient was randomized and reviewed at regular intervals by data analysts throughout the study period. The data analysts will have no participant contact and be blinded to study assignment. The EMR system is in place in our institution. All visit notes and diagnoses are to be entered within 48 hours of the encounter.

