Secondary outcome: Utilization is defined in terms of specialty visits, emergency room visits, and hospitalizations up to 12 months following the screening visit. This will be tracked via the EMR in both groups. The rates of utilization will be compared between the two groups using analytical approaches described for the primary outcome. We will also compare ‘days free of utilization’ (number of days from screening to first episode of health care utilization over follow-up) in both groups using linear mixed effect and survival models.^{58, 59}

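### The only secondary outcome, 12-month utilization, has two conflicting definitions, and section 9.5 does not commit to separating specialty visits from acute care

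*Combined protocol and SAP*

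**What the plan says.** Utilization is the only outcome labelled secondary; section 3 labels the neuropsychological battery and advance care planning exploratory. It is defined in four places.

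- Section 1.2, first sentence: "Utilization (emergency room visits and hospitalizations) for patients in both arms will be tracked and reviewed at regular intervals throughout the study period". The next sentence of 1.2 adds specialty visits, in the same words as 9.5.
- Section 3, item a: "Utilization (emergency room visits and hospitalizations) for patients in both arms will be tracked up to 12 months from the clinic visit".
- Section 9.4.2: "Health care utilization (emergency room visits and hospitalizations) for patients in both arms will be tracked up to 12 months from the clinic visit".
- Section 9.5: "Utilization is defined in terms of specialty visits, emergency room visits, and hospitalizations up to 12 months following the screening visit".

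Section 9.5 compares utilization rates by the methods used for the primary outcome. It also compares days free of utilization, described as the "number of days from screening to first episode of health care utilization over follow-up", "in both groups using linear mixed effect and survival models".

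On the intervention, section 9.2 says: "Red flags are built within our decision tree to channel patients for specialist evaluations". Section 9.4.1 (component 4) counts referral to Neurology, Geriatrics or Psychiatry as improved dementia care. The control arm also has a decision tree that goes to the physician (Précis, 5.1, 6.2.2), but its content is not given.

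**The concern.** The outcomes section and the analysis section disagree on which events count. Two analysts who both follow the plan could therefore report different secondary outcomes, and the choice is still open.

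The difference matters most for the time-to-first-event measure. If specialty visits count, the first one ends a patient's event-free time, and 9.5 does not limit these visits to any specialty. Specialist evaluation is also something the intervention is built to bring about. The same care pathway can then be a success in the primary outcome and shorten event-free time in the secondary one. A reader who sees a difference in days free could not tell whether acute care changed or intended referrals took place.

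A smaller point concerns the model. Each patient contributes one time, which is censored if no event occurs within 12 months. A standard linear mixed model is meant for repeated measurements and does not handle censoring.

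**Working it through.** **1. The texts side by side.** Emergency room visits and hospitalizations only: 1.2 (first sentence), 3a, 9.4.2. The same plus specialty visits: 1.2 (second sentence), 9.5. No section ranks the two, and the amendment log records no change to 1.2, 9.4.2 or 9.5. The conflict is in current text and needs no calculation.

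**2. Start of follow-up.** Sections 3a and 9.4.2 count from the randomization visit; 1.2 and 9.5 count from screening. In 9.2.1, screening appears to mean the randomized assessment itself. Under the COVID-19 procedure in 4.3, telephone screening falls on the day before the appointment. The gap is at most one day, so this is a point of wording.

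**3. Could the choice of definition matter numerically?** The plan gives no figure for this outcome, so there is nothing to reproduce. It gives no utilization rate, no proportion of referrals that become visits, and no content for the control tree. What follows is an illustration on assumed inputs.

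Assumptions:
- no effect on emergency room visits or hospitalizations;
- exponential time to first counted event, with 12-month risk *q* between 0.3 and 0.9 in both arms (wide, because any specialty may count);
- an added specialist visit at day *t* between 30 and 120, independent of the background event;
- *d* = the proportion of patients with an added visit, 5-Cog minus control;
- 540 per arm (600 less the 10% non-completion in 9.2, which the plan states for 90 days only).

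Formulas: λ = −ln(1−*q*)/365; R(*a*) = (1−e^(−λ*a*))/λ; change in mean event-free days = *d*·[R(365)−R(*t*)]; change in the proportion with any utilization = *d*·(1−*q*).

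With *t* = 60:
- *q* = 0.3: λ = 0.000977, R(365) = 307.0, R(60) = 58.3. One net point shifts the mean by 0.01 × 248.7 = 2.49 days.
- *q* = 0.9: λ = 0.006308, R(365) = 142.7, R(60) = 49.95. One net point shifts the mean by 0.01 × 92.7 = 0.93 days.

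Over *t* = 30 to 120, one net point shifts the mean by 2.77 days (*q* = 0.3, *t* = 30) down to 0.59 days (*q* = 0.9, *t* = 120). It shifts any-utilization by 0.7 down to 0.1 points. If both arms have the same added visits, the shift is zero.

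**4. Net excess at which the expected difference equals 1.96 standard errors.** The SD of event-free days truncated at 365 is 105.6 at *q* = 0.3 and 115.3 at *q* = 0.9.
- *q* = 0.3: 1.96 × 105.6 × √(2/540) = 12.6 days; at *t* = 60, 12.6/2.49 = 5.1 points.
- *q* = 0.9: 1.96 × 115.3 × √(2/540) = 13.8 days; at *t* = 60, 13.8/0.93 = 14.8 points.
- Over *t* = 30 to 120 the range widens to 4.5 points (12.6/2.77) to 23.5 points (13.76/0.585).
- For any-utilization, with a pooled two-proportion standard error, 8.0 points are needed at *q* = 0.3 (30% v 35.6%) and 33.0 at *q* = 0.9 (90% v 93.3%).

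With 600 per arm the days-free thresholds shrink by √(540/600) = 0.949, to about 4.3 to 22.3 points. Those for any-utilization become 7.6 to 31.4.

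**The case against.** The best defence is that counting specialty visits may be deliberate. The trial is pragmatic, and 9.2 promises to monitor the clinical, logistical and economic impact, naming strain on limited primary care resources as a major consequence of over-detection. Specialist visits caused by the intervention are then part of its effect on resource use, not contamination. Time to first utilization of any type is also protected by randomization. The component data should exist: "The detailed claims-level data will allow for tracking and analysis of the utilization of numerous healthcare services". All of this stands, and it rules out three stronger readings.

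- A reader might infer that the composite is uninterpretable or biased against 5-Cog. The documents do not support that. The contrast is valid; what it lacks is attribution by component. The 9.2 text covers red-flagged patients only, a referral is not an attended visit, and the control arm has its own tree. The net shift could go either way or cancel.
- A reader might infer that 9.4.2 must prevail. The only sentences that say utilization is *defined* a certain way, in 1.2 and 9.5, are the ones that include specialty visits. The documents require reconciliation but do not settle which way.
- A reader might infer that a competing-risks analysis is needed. Treating death as a competing event is a reasonable option, but the contradiction can be resolved without it.

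The defence does not remove the conflict itself. Nor does it supply a commitment in 9.5 to report the components. Such a breakdown of rates would in any case not separate the causes within a time-to-first-event measure.

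**Conclusion.** The point holds as a contradiction in current text: the trial's only secondary outcome has two definitions, and following the plan can give either. On the natural reading of 9.5, a first specialty visit ends event-free time. Section 9.5 says first episode without adding that any type counts, so this is an inference, though the obvious one. A between-arm difference would then be a valid contrast that cannot be attributed to acute care or to specialist visits unless components are separated.

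Size and direction cannot be determined from the documents. On the assumed inputs, each net percentage point of added visits moves mean event-free time by 0.6 to 2.8 days, and a net excess of roughly 4.5 to 23.5 points would be needed before the expected difference reached two-sided p = 0.05 at 540 per arm. Referrals alone may never produce a significant result, so the illustration demonstrates no bias. The contradiction is certain; its practical consequence is not. The sponsor should correct it, but it does not affect the primary analysis.

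**What to change.** Before unblinding:

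1. State one definition of utilization, in the same words, in 1.2, 3a, 9.4.2 and 9.5, counted from the randomization visit. The choice of definition is the sponsor's.
2. Whichever is chosen, analyse time to first emergency room visit or hospitalization separately, and report specialty visits as their own component. If the all-type composite is kept as a resource-use measure, show it alongside these.
3. Analyse days free of utilization with the survival model already planned, censored at 12 months, and drop the linear mixed model for it. Treating death as a competing event is optional.

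The cost is wording in four sections, one model fewer and a little more analysis. On section 3's account of the claims data, no new data collection should be needed. The real downside is that the acute-care comparison has fewer events than the composite and so less precision.

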9.4 Outcomes

9.4.1 Primary outcome

Our primary outcome is **improved dementia care**. This outcome is collected prospectively from EMR and related medical records by data analysts (Administrative & Statistics Cores) and do not require patient interviews. This primary outcome is defined as meeting any one of the following endpoints within 90 days of the clinic visit at which the patient was randomized. Similar composite endpoints to define dementia care have been used in several prior clinical trials in cognitively impaired patients.³²⁻³⁶

1. New diagnosis of dementia (relevant ICD-10 codes) or MCI (331.83) documented in the EMR. The recent DSM-V criteria³⁷ include categories of ‘major neurocognitive disorder’ and ‘mild neurocognitive disorder,’ which overlap with dementia and MCI. These categories will also be included but a recent internal audit indicated that they are as yet not in widespread use in our primary care clinics (cf. specialty clinics).
2. Tests ordered for reversible causes of cognitive impairment as recommended by the published guidelines of professional societies (e.g. thyroid function tests, B-12 level, CT or MRI scans).^{15, 38-41}
3. New prescriptions for dementia medications in EMR.
4. Referral for cognitive/dementia evaluation by specialists (Neurology, Geriatrics or Psychiatry) in EMR.

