9.5 Data Analyses

We will examine data for potential outliers and analyze the robustness of our findings

against them. We will perform per-protocol analysis to assess the sensitivity of our findings to protocol deviations. Furthermore, the impact of baseline imbalance will be determined by comparing the analysis outcomes with and without controlling for baseline attributes. Chi-square test will be used to compare ‘improved dementia care’ outcome within 90 days post-intervention between the intervention and control groups. Logistic regression model adjusted for covariates will also be used. We will use **intention to treat analysis**.⁵⁷ Pre-specified baseline covariates to account for **confounders** in the planned analysis include age, gender, education, and chronic illnesses. Baseline distribution of covariates will be compared to assess adequacy of randomization. We do not discount residual/unmeasured confounding – though this is more of an issue in observational studies without randomization. We will report adjusted and crude estimates of associations to assess confounding, and discuss limitations of the study.

Primary outcome: Chi-square test will be used to compare ‘improved dementia care’ outcome within 90 days post-intervention between the intervention and control groups. Logistic model adjusted for covariates will also be used.

Heterogeneity of treatment effect (HTE) is the nonrandom, explainable variability in the direction and magnitude of treatment effects for individuals within a population. The main goals of HTE analysis are to estimate treatment effects in clinically relevant subgroups and to predict whether an individual might benefit from a treatment. In this RCT, we will specifically address HTE due to gender (male/female), ethnicity (African-American/Hispanic/Caucasian) and education (less than high school/ high school graduate). Treatment effects in these subgroups will be evaluated using stratified analysis. Alternative, an interaction term between the subgroup characteristic and treatment group will also be tested.

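### The 12-month utilization rates are assigned yes/no methods, so the only secondary outcome has no analysis of visit frequency

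*Combined protocol and SAP*

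**What the plan says.** Section 9.5 defines the secondary outcome: "Utilization is defined in terms of specialty visits, emergency room visits, and hospitalizations up to 12 months following the screening visit". It then gives the comparison: "The rates of utilization will be compared between the two groups using analytical approaches described for the primary outcome". For the primary outcome the same section names two methods: "Chi-square test will be used to compare" the arms, and "Logistic model adjusted for covariates will also be used". The primary outcome is binary with a fixed window (section 9.4.1): "This primary outcome is defined as meeting any one of the following endpoints within 90 days of the clinic visit".

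Section 9.5 adds a second utilization analysis, days free of utilization, meaning the "number of days from screening to first episode of health care utilization over follow-up", to be compared "using linear mixed effect and survival models".

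Section 3 describes the data: "The detailed claims-level data will allow for tracking and analysis of the utilization of numerous healthcare services". No section names a count model, a person-time offset, or an overdispersion or robust variance. None gives a rule for turning visits into a binary variable.

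**The concern.** Specialty visits, emergency visits and hospitalizations can each occur several times in a year. A rate has a count on top and observed time below. The methods that section 9.5 points to use neither: a patient with one visit is scored the same as a patient with eight, and a patient who dies or leaves in month 2 without a visit is scored as a full year without use. The survival analysis handles early exit, but only up to the first episode.

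This is the only outcome labelled secondary. As written, the trial could report whether 5-Cog changes the chance of any use and the time to first use, but would have no pre-specified estimate of whether it changes how often patients use care.

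**Working it through.** **The plan's own figures.** The documents give no visit rate, dispersion, effect size or power for utilization. The power statement in section 9.2 concerns the primary outcome, and it reproduces. With 600 × 0.9 = 540 per arm, the odds ratios giving 80% power are 1.459, 1.434 and 1.419 at control rates of 25%, 30% and 35%, against the stated 1.46, 1.43 and 1.42. Nothing below affects it.

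**Inputs.** From section 9.2: 600 per arm, two-sided 0.05. Assumed: visit counts with mean μ per patient-year and variance μ + kμ², with μ from 0.5 to 2 and k from 0.5 to 3, and a true rate ratio of 0.75.

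**Step 1: one worked case (μ = 1, k = 1, 540 per arm, full follow-up).**

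- Proportion with any use = 1 − (1 + kμ)^(−1/k). Control: 1 − 1/2 = 0.500. Intervention: 1 − 1/1.75 = 0.429.
- Any-use chi-square: difference 0.0714, null standard error √(2 × 0.464 × 0.536/540) = 0.0304, alternative standard error 0.0303. Power = Φ((0.0714 − 1.96 × 0.0304)/0.0303) = 65%.
- Negative binomial rate comparison: variance of the log rate ratio = [(1/1 + 1) + (1/0.75 + 1)]/540 = 0.00802, standard error 0.0896. Power = Φ(0.2877/0.0896 − 1.96) = Φ(1.25), about 90%.

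**Step 2: the assumed grid.** Over all the values of μ and k, power runs from 30% to 79% for any use and from 54% to 99% for the rate model. The rate model is ahead in every cell under this form of effect.

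**Step 3: simulation at 600 per arm with early deaths.** Gamma-Poisson counts, 5% mortality in both arms, (mean, gamma shape) = (0.8, 0.5), (0.8, 1.0) and (1.2, 0.7).

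| Scenario | Any-use chi-square | Patient-level rate model |
|---|---|---|
| Constant rate ratio 0.75: power | 50-66% | 76-88% |
| All use removed in 25% of intervention patients: power | 93-99% | 71-85% |

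With no effect, the any-use test rejects 4.8-5.6% of the time, so it is valid here.

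**Step 4: unequal follow-up (μ = 1, k = 1, equal true rates, 540 per arm).** With 10% leaving early in both arms, rejection is 4.3% for any use and 4.9% for a person-time comparison with robust variance. With 5% against 15% leaving early, it is 9.5% and 5.2%.

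**The case against.** The strongest reply is that the protocol uses the word rates for proportions of patients elsewhere, as in the expected rates of improved care among controls (section 9.2) and of advance care planning (section 3). Read that way, the sentence plans an any-use comparison. That is a legitimate estimand and the test is valid for it. The same paragraph also plans a survival analysis that can censor at death or loss. The power advantage of a count model depends on the form of the effect, and the second row of the table shows it reversing. All of this stands, and it limits the point to a mismatch between quantity and method plus a conditional loss of power.

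It does not remove the point. The any-use rule is not written down, and on either reading visit frequency has no planned analysis.

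A reader might go further in two ways that the documents do not support.

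- **Inflated type I error.** A chi-square on visit totals, treating each visit as independent, would reject too often when visits cluster within patients: 2(1 − Φ(1.96/√(1 + kμ))), or about 17% at μ = 1, k = 1. No section plans that test, and the cross-referenced methods work on patients, not visits.
- **Bias from ignoring person-time.** This needs follow-up to differ between arms. Section 8 permits withdrawal at any time, but nothing suggests a difference by arm. Outcomes come from EMR and claims data, including some care from outside providers.

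**Conclusion.** The concern holds in a limited form. Section 9.5 promises a comparison of rates and assigns methods that can compare only any use with none; the added survival analysis does not reach repeat visits. The any-use test keeps its error rate when follow-up is similar in the two arms. What is lost is the stated quantity and, under a constant rate ratio of 0.75, roughly 20 to 25 percentage points of power (50-66% against 76-88%). That size rests on assumed visit rates, dispersion and mortality and on the assumed form of effect, so it is illustrative. The case for change rests mainly on matching the method to the rate. The change is worth making because it is cheap, but the primary inference does not depend on it.

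**What to change.** First reconcile what counts as utilization. Section 9.5 includes specialty visits; sections 3 and 9.4.2 list only emergency visits and hospitalizations; section 1.2 contains both versions. This matters because the decision tree can itself lead to specialist referral, so specialty visits could rise in the 5-Cog arm while other use falls. Use one clock start as well: section 9.5 counts from screening, sections 3 and 9.4.2 from the visit of randomization.

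Then replace the sentence with:

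*Visits per person-year from the randomization visit, by type, will be compared by a patient-level negative binomial model (or Poisson model with robust variance) with log observed time as offset, adjusted for the stratification factors and the pre-specified covariates, reporting rate ratios with 95% confidence intervals. Any use (chi-square and logistic regression) and time to first episode (survival model) are supportive. Visit totals will not be tested as independent events.*

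The covariates are those already in section 9.5: age, gender, education and chronic illnesses.

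The cost is small. Claims-level utilization data are already planned (section 3) and date of death is a listed data element (section 10.2), so no new collection is needed. The team takes on slightly more analysis work, any use moves to a supportive role, and the plan should say which visit type leads or that the rate ratios by type are reported without a multiplicity claim. The offset treats death as uninformative, which should be stated as a limitation.
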